12.0 ADVERSE EVENTS

12.1 Definitions

Adverse Event

For this study, an adverse event is defined as any undesirable clinical occurrence in a patient that is determined to be device-related or procedure-related by the Investigator. All AEs that meet this definition are to be recorded in the eCRF and reported to the Sponsor. All SAEs, regardless of relationship to the study device or procedure, are to be collected.

The Sponsor will review all applicable site-reported AEs and SAEs according to the current Safety Monitoring Plan.

Expected Morbidity/Anticipated Adverse Events

An expected morbidity/procedural complication is defined as an AE that is known to be common or usual in nature, severity, or incidence during ablation of the liver.

Serious Adverse Event

It is the Investigator's responsibility to determine the "seriousness" of an AE using the protocol defined terms below. An SAE is an AE that results in one or more of the following for this study:

- Life-threatening: The patient was at imminent risk of dying at the time of the adverse event.
- Permanent Impairment: An AE that resulted in permanent impairment of a body function or permanent damage to a body structure.
- Necessitated Intervention: An AE that resulted in a condition that necessitated medical or surgical intervention to preclude permanent impairment of a body function or damage to a body structure.
- Required in-patient or prolonged hospitalization.
- A persistent or significant disability or incapacity.
- Resulted in death: An AE that resulted in the patient's death.

Notes:

1. Progression of the disease under study should not be reported as an SAE.
2. "Death" should not be reported as an AE. The cause of death should be reported as an SAE. The only exception is "Sudden Death" when the cause is unknown.
3. Planned hospitalization for a pre-existing condition is not considered an SAE.

Severity of Adverse Events

It is the Investigator's responsibility to assess the severity of an AE. A change in severity of a pre-existing medical condition or of a current AE may constitute a new reportable AE.

In addition, the following guideline may be used to determine the severity of each AE:

- **MILD:** Awareness of signs or symptoms but does not interfere with the patient's usual activity or is a transient event that resolves without treatment and with no sequelae.
- **MODERATE:** A sign or symptom which interferes with the patient's usual activity.
- **SEVERE:** Incapacity with inability to do work or usual activities.

Relationship of Adverse Events

It is the Investigator's responsibility to assess the relationship between all AEs and the study procedure and device. Adverse events deemed to have a possible, probable, or causal relationship to the procedure or device should be captured in source as part of the study and entered into the AE eCRF. AEs deemed to be Not Related to the procedure or device will be noted in source only. The following guidelines should be used in determining the relationship of an adverse event to a device, study procedure, or other causality:

Not Related	
Relationship to the procedure or device can be excluded when:
 
 • The event is not a known side effect of the product category the device belongs to or of similar device and procedures; • The event has no temporal relationship with the use of the device or the procedures; • The event does not follow a known response pattern to the device (if the response pattern is previously known) and is biologically implausible; • The discontinuation of the device application or the reduction of the level activation/exposure (when clinically feasible) and reintroduction of its use (or increase of the level of activation/exposure), does not impact on the event; • The event involves a body-site or an organ not expected to be affected by the device or the procedure; • The event can be attributed to another cause (e.g., an underlying or concurrent illness/clinical condition, an effect of another device, drug, treatment, or other risk factors); • Harms to the subject are not clearly due to use error; or • To establish the non-relatedness, not all the criteria listed above might be met at the same time, depending on the type of device/procedure and the event.
Possible*	
The relationship with the use of the device is weak but cannot be ruled out completely. Alternative causes are also possible (e.g., an underlying or concurrent illness/condition and/or an effect of another device, drug, or treatment). Cases where relatedness cannot be

	assessed, or no information has been obtained should also be classified as possible.
Probable*	The relationship with the use of the device seems relevant and/or the event cannot reasonably be explained by another cause, but additional information may be obtained.
Causal Relationship*	
The event is associated with the device or with procedures beyond reasonable doubt when:
 
 • The event is a known side effect of the product category the device belongs to or of similar device and procedure • The event has a temporal relationship with the device uses/application or procedures • The event involves a body-site or organ that 
 ◦ The device or procedures are applied to ◦ The device or procedures have an effect on • The event follows a known response pattern to the medical device (if the response pattern is previously known) • The discontinuation of medical device application (or reduction of the level of activation/exposure) and reintroduction of its use (or increase of the level of activation/exposure), impact on the event (when clinically feasible) • Other possible causes (e.g., an underlying or concurrent illness/clinical condition and/or an effect of another device, drug, or treatment) have been adequately ruled out • Harm to the subject is due to error in use • To establish the relatedness, not all the criteria listed above might be met at the same time, depending on the type of device/procedure and the event.

*Indicates definitions of relationship that qualify to be recorded as part of the study for AEs only. All SAEs, regardless of relationship, will be collected.

12.2 Reporting Adverse Events

All procedure-related and device-related AEs from the time of the first probe puncture (Visit 2) through study completion (Visit 3), or from the time of early withdrawal of the study, must be reported in the AE eCRF.

The Investigator is required to report all applicable non-serious AEs to the Sponsor within 2 weeks of becoming aware of the adverse events. All SAEs, regardless of relationship to the study device or procedure, are to be reported as soon as possible, but no later than 72 hours after becoming aware of the event, regardless of relationship to the device or study procedure.

The study site will report applicable AEs and all SAEs to the Sponsor by entering the event into the EDC system via the Adverse Event eCRF, which will trigger an automated email to the Sponsor. Additional information, including the Investigator's assessment, may be added to the eCRF later. Any necessary medical management of the event will be recorded in the patient's medical record/source document. If the Sponsor requires

supporting documentation or other information, the Sponsor will contact the study site.

Data related to AEs and SAEs will be collected until event resolution, until the event is considered stable, or until all attempts to determine the resolution of the event are exhausted. All AEs and SAEs that are unresolved at study completion (or early termination) will be recorded as ongoing at study end.

In addition, the following information should be recorded:

- Onset date.
- Resolution date or date of death.
- Severity of the event.
- Action taken.
- Event status (ongoing at study end or resolved).
- Relationship of AE to the ablation device used in the study.
- Relationship of AE to the study procedure.
- Indication of seriousness.
- Was AE anticipated or not.

The report of an AE or SAE by a site does not constitute an admission that study personnel or the user facility (hospital/clinic) caused or contributed to the event. The site is responsible for submitting AEs to the reviewing IRB/EC, per their IRB/EC procedures.

13.0 PRODUCT COMPLAINTS

13.1 Product Complaint Definition

A product complaint is defined as any written, electronic, or oral communication that alleges deficiencies related to the identity, labeling, quality, durability, reliability, safety, effectiveness, or performance of a device after it is released for distribution (21CFR 820.3 (b)). A product complaint may or may not be associated with an AE/SAE.

Product complaints may include, but are not limited to:

1. Product contamination;
2. Defective components;
3. Device malfunction (the failure of a device to perform as intended for this study);
4. Poor packaging or product mix-up;
5. Labeling concerns;
6. User errors.

13.2 Reporting Product Complaints

All product complaints related to devices in the procedure shall be documented throughout the clinical investigation.

The study site must report product complaints related to a device manufactured by NeuWave Medical, Inc., in a timely manner after becoming aware of the event.

When any representative of the Sponsor becomes aware of a product complaint, the Sponsor representative must notify the Sponsor's Product Complaint Team With the least practical delay of becoming aware of information (if immediate reporting is not possible).

The Product Complaint Form must be emailed to the Sponsor Customer Complaint team at the following email address: [contact]. One copy of the processed form should be kept on-site, and the device should be retained. Sponsor representatives will organize collection of the device for evaluation, as needed.

The product complaint may also be reported by calling [name].

14.0 PUBLICATION PLAN

[figure not shown]
Publication and authorship policies should be determined and aligned with the clinical study agreement executed between operating company and each clinical site. Publication of the results of this study will be governed by J&J publication policies, including current and applicable Medical Device Publication Policy. Any presentation, abstract, or manuscript will be made available for review by the Sponsor prior to submission. Licensing agreements or copyrights applying to tools, work products or intellectual property used during the study should be observed and clearly displayed on study documentation and publications, wherever appropriate.

All manuscripts of data obtained from this clinical study will be reviewed and approved by the Sponsor, and each author, prior to any submission. Current and applicable Medical Device Publication Policy will be followed. The Sponsor will require a written agreement for any external author(s) prior to initiating any publication. All authors must disclose financial or personal affiliations that could be considered a conflict of interest.

15.0 APPENDICES

APPENDIX 1: NUMERIC PAIN RATING SCALE

For the Numeric Pain Rating Scale (NPRS), the patient is asked to indicate the numeric value on the segmented scale that best describes his or her pain intensity.

APPENDIX 2: ABLATION CONFIRMATION USER EVALUATION QUESTIONNAIRE

A Multicenter Study to Evaluate NEUWAVE Microwave Ablation System Using Ablation Confirmation in Patients with A Soft-tissue Liver Lesion

Protocol Number: NEU_2017_03

The Ablation Confirmation User will complete the table below after each ablation:

Please grade, on a scale of 0 to 5 (strongly disagree to strongly agree), how helpful AC was with the following:

Procedure Step	Definition	AC Helped Me (0-5 scale)	Comments
Lesion Visualization	Marking and tracking the target (How well the target lesion can be seen in the tissue.)		
Approach Planning	Planning needle position (Optimal path selection and ablation coverage optimization.)		
Probe Placement	Understanding probe position prior to ablation (The entry and movement traversing until in final position.)		
Ablation Planning	Determining power and time to deliver to cover target and desired margin (Probe, time, power, tissue contraction [tissue type])		
Ablation Confirmation	Evaluating technical success of ablation coverage of target plus margin (Determination of zone of effective ablation compared to target lesion and desired margin)		

The below is completed after approximately every 5 patients are treated by the performing physician (i.e., 5 patients are ablated with the NeuWave Microwave Ablation System with Ablation Confirmation Software).

Please grade, on a scale of 0 to 5 (Strongly disagree to strongly agree), how helpful AC was with the following:

- AC did not have a significant impact on procedure time or case resources. _____
- I use AC in every case because it increases my confidence in achieving a successful ablation. _____
- Ablation with NeuWave Microwave is more predictable, consistent, and controllable than other thermal ablation technologies. _____
- Ablation with multiple NeuWave probes is faster and more consistent than repeated place and ablate cycles with other thermal ablation technologies. _____
- Ablation with NeuWave Microwave increases my confidence in achieving a successful ablation compared with other thermal ablation technologies. _____

Additional comments not already captured above:

This is the Statistical Analysis Plan (SAP) for the final analysis of data collected under Protocol NEU_2017_03. This SAP describes, in detail, the statistical methodology and statistical analyses for the above-mentioned protocol.

1 Study Overview

1.1 Study Objectives

The primary objective of the study was to examine whether the feedback from the AC software impacts the performing physician's (i.e., the individual performing the ablation procedure) decision making in terms of probe(s) position, ablation time, or number of ablations based on insufficient ablation margins based on the following assessments:

- a. Percentage of repositions informed by AC due to sub-optimal probe placement.
- b. Percentage of re-ablations informed by AC due to insufficient ablation margins.

The secondary objectives were the following:

1. Technical success - defined as ablation of the target lesion(s) according to the protocol and covered completely with an adequate margin, as defined by the performing physician (that is, the ablation zone completely overlaps or encompasses the target lesion plus an adequate ablative margin). Technical success will be assessed by the performing physician using AC as a tool immediately following the procedure.
2. Technique efficacy - defined as ablation of the target lesion(s) according to the protocol and covered completely, with an adequate margin, as defined by the performing physician (that is, the ablation zone completely overlaps or encompasses the target lesion plus an ablative margin), as assessed by imaging at Visit 3.
3. Hospital resource utilization based on:
 - a) Length of post-ablation hospital stay.
 - b) Time to perform procedure, which includes 3 measures of time:
 - Overall procedure duration, defined as the time elapsed between loading CT dataset into the AC system and completion of MWA with last probe removal.
 - AC imaging duration, defined as the time elapsed between loading CT dataset into AC to plan for the target ablation and last use of AC to plan for the final ablation.
 - Ablation duration, defined as the time elapsed between ablation first probe puncture and removal of the last probe at the completion of the ablation.
4. Device and procedure safety through the monitoring of adverse events. Patients will be evaluated for all device-related and procedure-related AEs and all SAEs from the time of the first probe puncture (Visit 2) through study completion (Visit 3).
5. Device User Experience questionnaire will be completed by the performing physician. The first half will be completed following each ablation procedure and the second half will be completed approximately every 5 ablations (per treating physician).

6. Patient Quality of Life (QOL) questionnaires as measured by EORTC QLQ-C30 and the liver-specific QLQ-HCC18, at Visit 2 (Pre-Ablation) and at Visit 3 (6 weeks post-ablation).
7. Patient Numeric Pain Rating Scale (NPRS) questionnaire at Visit 2 (Pre- and Post-Ablation) and at Visit 3 (6 weeks post-ablation).

1.2 Study Design

This was a prospective, single-arm, multicenter clinical study that generated clinical data using NEUWAVE Microwave Ablation System with Ablation Confirmation Software in patients undergoing MWA of at least one soft-tissue liver lesion as part of the study site's SOC treatment.

2 Treatment Assignment

This was a single-arm study where all enrolled patients were ablated using the NEUWAVE Microwave Ablation System and the AC software tool.

3 Randomization and Blinding Procedures

This is a single-arm, open-label study. No randomization occurred and no blinding procedures were required.

4 Interval Windows

Interval windows are not defined for the purpose of analysis in this study outside of the visit windows that are provided in the Schedule of Assessments in Table 1 of the final protocol. There will be no assigning of observations to time points outside of the visit to which they are recorded in the electronic Case Report Forms (eCRFs). Data collected in Unscheduled Visit forms will be listed as such.

5 Level of Significance

No hypotheses are specified for this study and no p-values are being calculated. Therefore, no level of significance is specified. For selected endpoints 95% confidence intervals will be estimated.

6 Analysis Sets

The study protocol identified two analysis sets:

- The Full Analysis Set (FAS) will consist of all eligible patients who are enrolled in the study and had the ablation procedure attempted with the AC tool. Lesions from patients in FAS that had the ablation procedure attempted with the AC tool will be included on the FAS. The FAS will be the primary analysis set for safety and effectiveness endpoints. Patients followed by lesions for whom the response was "Yes" to the question "Was

ablation confirmation software used to validate probe placement?” on the Ablation Confirmation form on the eCRF will be included on the FAS.

- The Per Protocol Analysis Set (PPS) will consist of all patients who are enrolled in the study and had the AC tool utilized as part of the ablation procedure with no major protocol deviations that indicate an exclusion from PPS. Lesions from patients in PPS that had the ablation procedure attempted with the AC tool will be included on the PPS. Effectiveness analyses is planned to be repeated for the PP Set. Patients followed by lesions for whom the response was “Yes” to the question “Was ablation confirmation software used to validate probe placement?” on the Ablation Confirmation form on the eCRF and had no major protocol deviations that indicate an exclusion from PPS as per the Protocol Deviation Classification document will be included on the PPS.

7 Sample Size Justification

Given that this was an initial experience with the AC system in a general use population, a sample size of a minimum of 100 patients was deemed sufficient for estimating the repositioning rate for appropriate sizing of a subsequent study. With an expected repositioning rate of 15%, a sample size of 100 patients would control the half-width of a 95% confidence interval to less than 7%. However, the study was terminated early with a smaller number of patients enrolled than planned. The reasons for early termination are difficulty in enrolling patients to the study and other studies are gathering similar data as the current study to help inform the objectives of the current study.

8 Data Safety Monitoring Board

This study did not use a DSMB.

9 Analyses to be Conducted

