8.2 Visit 2 – Ablation Procedure

The following procedures will be done before the ablation procedure:

- Evaluate ECOG performance status.
- QOL questionnaires: EORTC QLQ-C30 and the liver-specific QLQ-HCC18.
- Pain score, using the Numeric Pain Rating Scale.
- Record any new relevant concomitant medications or changes to existing relevant concomitant medications (i.e., blood-thinning/coagulation, NSAIDs, steroids, and medications used to treat hepatitis, if concurrently treating).
- Record any new liver-related concomitant procedures.
- Confirm that the patient still meets inclusion and exclusion criteria (tests not needed to be repeated).
- Serum urine pregnancy test, per site SOC, for women of childbearing potential only.
- Complete blood count, with differential (RBCs, WBCs, platelets, hemoglobin, hematocrit, neutrophils, etc.). Use CT to collect lesion details: e.g., size of lesion, lesion type, location, shape. If unable to accurately visualize the lesion with non-

contrast enhanced CT, contrast enhanced CT must be used. Note: the Screening Visit CT and Visit 2 CT may occur on the same date if the patient was screened and treated on the same day.

- Use AC to define the target lesion(s). The final visualization of the target lesion should be documented using the AC snapshot feature to capture the contents of the imaging panels.
- Develop a treatment plan to perform the MWA of the patient's liver lesion(s) and capture the details of the treatment plan (probe(s) planned to be used, liver segment(s), max power planned, and total ablation time planned) in the study database. Note: A patient cannot have more than three lesions ablated during the procedure.
- After the patient is sedated under general anesthesia or deep conscious sedation, and administered antibiotics, if applicable, per SOC, the performing physician will place the probe in position without the use of Ablation Confirmation. Probe placement may be performed using either ultrasound or CT scan.

The following procedures will be done during the ablation procedure:

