iii) Ablation duration, defined as the time elapsed between ablation first probe puncture and removal of the last probe at the completion of the ablation. Ablation duration is captured on the Ablations form on eCRF under the variable name “Duration.”

Other endpoints associated with hospital resources utilization will be listed.

4. Device-related and procedure-related AEs and all SAEs from the time of the first probe puncture (Visit 2) through study completion (Visit 3 or early termination from the study) will be summarized based on FAS. Further details on safety analysis are presented on Section 9.5.

5. Device User Experience questionnaire: It is measured by the “Ablation Confirmation User Evaluation Questionnaire” and completed by the performing physician. The first half will be completed following each ablation procedure and the second half will be completed approximately every 5 ablations (per treating physician). The questionnaire will be summarized by its items for the frequencies and corresponding percentages based on the FAS. A listing will be provided for the Ablation Confirmation User Evaluation Questionnaire.

6. Patient Quality of Life questionnaires: Quality of Life will be measured using EORTC QLQ-C30 and liver specific QLQ-HCC18 at Visit 2 (pre-ablation) and Visit 3.

C30 and HCC18 overall scores will be derived to have an overall representation of all domains/items in QLQ-C30 and QLQ-HCC18, respectively. The scores for C30 and HCC18 will be derived as per the guidance on the European Organization for Research and Treatment of Cancer (EORTC) QLQ-C30 scoring manual version 3.0.

The overall scores for each scale and the changes from Visit 2 to Visit 3 will be summarized using N, mean, standard deviation, minimum, maximum, and median based on the FAS. The overall scores for each scale will be listed.

EORTC QLQ-C30:

The EORTC QLQ-C30 (version 3.0) comprises 30 questions and provides a multi-dimensional assessment of QoL.

The QLQ-C30 is composed of both multi-item scales and single-item measures. EORTC QLQ-C30 can be combined to produce 5 functional scales (Physical, Role, Cognitive, Emotional, Social), 3 symptom scales (Fatigue, Pain, Nausea/vomiting), 5 individual items (dyspnea, insomnia, appetite loss, constipation, diarrhea) and a global measure of health status.

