9.5 Safety Analyses

Safety will be assessed through the incidence of AEs and SAEs, which will be coded using MedDRA. The number and percentages of patients reporting AEs and SAEs will be summarized at the MedDRA system organ class and preferred term level. As a secondary endpoint of the study summaries will be provided for AEs and SAEs related to the study device, as well as for AEs and SAEs related to the study procedure. Related events are those where the relationship is indicated as Possible, Probable, or Causal relationship. Summaries of all AEs and SAEs reported within the first 30 days after the initial ablation procedure will be generated. All reported adverse events will be listed. Listings will also be provided for concomitant procedures and concomitant medications.

Safety endpoints are as follows:

- All AEs
- Serious AEs
- All AEs related to the study device
- Serious AEs related to the study device
- All AEs related to the study procedure
- Serious AEs related to the study procedure

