9.8 Handling of Missing Data

All analyses will be performed only on patients who had the ablation procedure with the AC software tool attempted and only observed data will be analyzed. There will be no imputation of missing data for any parameters or for early terminated patients.

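### AE and SAE tables run on a set chosen by use of the AC software, so a patient injured at probe puncture before AC review can drop out of them

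*SAP*

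**What the plan says.** SAP section 6 defines two sets, the FAS and the Per Protocol Set, and neither is a safety set. It states: "The FAS will be the primary analysis set for safety and effectiveness endpoints". In words, the FAS is "all eligible patients who are enrolled in the study and had the ablation procedure attempted with the AC tool". The same paragraph then gives a selection rule: patients and lesions with a *Yes* on the Ablation Confirmation form to the question whether AC was used, in the form's words "ablation confirmation software used to validate probe placement".

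SAP 9.4.2 item 4 puts the safety endpoint on this set. The events to be summarised are "Device-related and procedure-related AEs and all SAEs from the time of the first probe puncture (Visit 2) through study completion". SAP 9.8 adds a general restriction: "All analyses will be performed only on patients who had the ablation procedure with the AC software tool attempted". Listings are wider, since SAP 9.5 says "All reported adverse events will be listed" and SAP 9.1 lists eCRF data for every patient.

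The arrangement comes from the protocol. Section 10.7 assigns safety to the FAS, and the missing-data paragraph of 10.9 limits all analyses to patients undergoing ablation with AC. On the order of steps, Protocol 8.2 says "the performing physician will place the probe in position without the use of Ablation Confirmation"; the scan and the AC review of placement come afterwards.

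**The concern.** A safety denominator should contain everyone exposed to the risk from the moment event counting starts. Here counting starts at puncture, but membership of the set depends on a later step, AC validation of placement, which a complication at puncture can prevent. A patient can therefore leave the AE/SAE tables because of the very outcome those tables report.

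Protocol 6.7 makes this a foreseen case. It describes a patient with a related AE or any SAE at puncture who is not ablated, and has that patient followed to resolution. The data are collected, but under the eCRF rule they do not reach the incidence tables. An event type seen only in such a patient would be absent from the system organ class and preferred-term table and would appear only in a listing.

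The eligibility condition in the FAS adds a second gap: a patient who was treated and is later judged ineligible is also removed from the safety tables.

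**Working it through.** The plan states no safety rate or precision target. Its only design figure, a 95% half-width below 7% for a 15% repositioning rate with 100 patients, reproduces (1.96 × √(0.15 × 0.85 / 100) = 6.998%) but does not bear on this point. The check is therefore a reading of the definitions, followed by an illustration.

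**1. Order of events against the selection rule**

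| Step | Source | AE/SAE counting | eCRF answer that admits to the FAS |
|---|---|---|---|
| Target defined with AC | Protocol 8.2, before ablation | not started | not yet available |
| Probe placed without AC | Protocol 8.2, before ablation | starts at first puncture | not yet available |
| Scan, then AC review of placement | Protocol 8.2, during ablation | running | can now be *Yes* |
| Ablation and AC margin check | Protocol 8.2, during and after ablation | running | already decided |

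A patient whose procedure stops between the second and third rows is at risk and under AE collection, but cannot have a *Yes*.

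**2. The two FAS definitions compared**

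The worded definition turns on the procedure having been attempted with AC. Because AC may already have been used to define the target, that wording can include this patient; the eCRF rule leaves the patient out. SAP 6 does not say which prevails. The eligibility condition in the worded definition excludes treated but ineligible patients on either reading of *attempted*.

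**3. Whether other text closes the gap**

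- Protocol 6.6 records consented patients whose ablation was not initiated as screen failures. It does not say whether a puncture counts as initiation.
- SAP section 2 says all enrolled patients were ablated. Under Protocol 6.2 enrolment is at consent, and 6.6 provides for consented patients who are not ablated, so that sentence cannot serve as a count.

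**4. Direction**

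Let the FAS have x patients with an event out of N, and let the punctured patients outside it have e out of m. The rate over all punctured patients, (x + e)/(N + m), exceeds x/N exactly when N(x + e) > x(N + m), that is, when e/m > x/N. The FAS rate is too low only if events are more frequent among the excluded patients than in the FAS.

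**5. Size under assumptions**

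The final N is not given; SAP 7 says only that "the study was terminated early with a smaller number of patients enrolled than planned". Assume N = 25, 50 or 75, a FAS SAE rate of 4%, and one excluded patient. Exact (Clopper-Pearson) 95% limits are in brackets.

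| N | FAS | Excluded patient had an SAE | Excluded patient had none |
|---|---|---|---|
| 25 | 1/25 = 4.0% (0.10 to 20.35) | 2/26 = 7.7% (0.95 to 25.13) | 1/26 = 3.8% (0.10 to 19.64) |
| 50 | 2/50 = 4.0% (0.49 to 13.71) | 3/51 = 5.9% (1.23 to 16.24) | 2/51 = 3.9% (0.48 to 13.46) |
| 75 | 3/75 = 4.0% (0.83 to 11.25) | 4/76 = 5.3% (1.45 to 12.93) | 3/76 = 3.9% (0.82 to 11.11) |

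- Three excluded at N = 50: 2/53 = 3.8% (0.46 to 12.98) if none had an event; 3/53 = 5.7% (1.18 to 15.66) if one did.
- Event type absent from the FAS: 0/50 (upper limit 7.11%) becomes 1/51 = 2.0% (0.05 to 10.45).
- Higher base rate, 50 punctured patients with 5 events in the FAS: with one patient outside, the FAS shows 5/49 = 10.2% against 5/50 = 10.0% to 6/50 = 12.0%; with five outside, 5/45 = 11.1% against 5/50 = 10.0% to 10/50 = 20.0%.

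**The case against.** The best defence is the wider reading. The SAP speaks of a procedure attempted with AC, AC is used on the target before any probe goes in, ablation duration is timed from first puncture, and Protocol 6.7 treats these withdrawals as occurring during the procedure. On that reading a punctured patient is in the FAS, and the eCRF sentence says who is included without saying that nobody else is. This shows that the exclusion is not certain. It does not rescue the plan, because the eCRF answer is the only operational selector the SAP gives, and the eligibility condition applies either way.

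It is also fair that every event is listed, that no safety threshold or test depends on the rate, that the exact intervals above overlap almost entirely, and that nothing in the documents shows even one affected patient. These points limit the importance of the issue. But safety is a stated secondary endpoint reported as numbers and percentages, and a listing gives no incidence. Protocol 6.7 does say how the punctured patient is followed; it does not place that patient in an analysis set.

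Two objections concern the remedy and stand as cautions. The documents show no eCRF field that records a puncture in a patient who was not ablated. And Protocol 6.7 has punctured, unablated patients without an event discontinued, so they would enter the denominator with little follow-up.

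**Conclusion.** The concern holds. Applied as written, the eCRF rule lets a complication at puncture remove a patient from both numerator and denominator of the AE/SAE tables, and no other set restores that patient. At an assumed FAS of 50 with a 4% SAE rate, one excluded event adds 1.9 points (4.0% to 5.9%), and one excluded non-event subtracts 0.1 (4.0% to 3.9%). At an assumed 25 the excluded event adds 3.7 points, and at 75 it adds 1.3. The number excluded, the event rate and the final N are all assumptions, the net direction is unknown, and with no such patients the tables do not change. Confidence is high that the definitions permit the exclusion; whether it occurred cannot be told from the documents. This should be fixed because it is cheap and removes an outcome-dependent exclusion, but it concerns a descriptive secondary endpoint only.

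**What to change.** - Add a Safety Set to SAP 6: all enrolled patients with at least one study-probe puncture, regardless of eligibility, AC use or completion of ablation.
- Use it as the denominator for all AE/SAE tables under SAP 9.4.2 item 4 and 9.5. The 30-day summary in 9.5 counts from the initial ablation procedure, so state the start date used for patients who were punctured but not ablated.
- Limit the restriction in SAP 9.8 to effectiveness analyses, and keep the FAS for those.
- Reconcile the worded FAS definition with the eCRF rule, so that one rule decides membership.
- State that a punctured patient is not removed from the safety tables as a screen failure under Protocol 6.6.
- Report how many punctured patients fall outside the FAS, with their events and length of follow-up. If the number is zero, that settles the matter.
- Document the change as a departure from Protocol 10.7 and 10.9.

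The cost is one population flag, re-run AE/SAE tables, SAP wording, and a note in the study report. Events are already collected from first puncture, so no new event data are needed. The sponsor should confirm that puncture can be identified from the eCRF or source records for patients who were not ablated. The listings need no change.
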